- Left ventricular ejection fraction by visual estimate

[figure not shown]
Qualitative grading of valvular regurgitation will be performed using the criteria described in Sections 4.4 through 4.6. For reporting the degree of prosthetic regurgitation, the grading classes may be collapsed according to the 3-class grading scheme recommended by the American Society or Echocardiography (ASE)-European Association of Cardiovascular Imaging Guidelines.³⁹

In addition, the following variables will be derived by the central database from the appropriate measurements reported by the Echo Core Lab:

Peak Pressure Gradient (Peak Δ P) Across the Aortic Valve in mmHg Peak Δ P = 4 x (V₂²)

Where: V2 is the peak velocity across the prosthesis in m/sec

Aortic Valve Area (AVA) in cm²

Medtronic

AVA = LVOT diameter in cm² x 0.785 x (VTI_{V1}/VTI_{V2})

Where: VTI_{V1} is the velocity time integral of the left ventricular outflow tract in cm, and VTI_{V2} is the velocity time integral of the native aortic valve in cm

 Aortic Valve Area Index (AVAI) in cm²/m² AVAI = AVA/BSA

Where: AVA is the native aortic valve area in cm², and BSA is the body surface area in m²viii

Effective Orifice Area (EOA) in cm²
 EOA = LVOT diameter² x 0.785 x (VTI_{V1}/VTI_{V2})

Where: VTI_{V1} is the velocity time integral of the left ventricular outflow tract in cm, and VTI_{V2} is the velocity time integral of the aortic prosthesis in cm

 Effective Orifice Area Index (EOAI) in cm²/m² EOAI = EOA/BSA

Where: EOA is the effective orifice area in cm², and BSA is the body surface area in m²

• Doppler Velocity Index (DVI)

 $DVI = VTI_{V1}/VTI_{V2}$

Where: VTI_{V1} is the velocity time integral of the left ventricular outflow tract in cm, and VTI_{V2} is the time velocity integral of the prosthetic aortic valve in cm

Estimated Right Ventricular Systolic Pressure (RVSP) in mmHg

 $RVSP = (4 \times MVTR jet^2) + 10$

Where: MV TR jet is the max velocity of the tricuspid regurgitant jet, and 10 = the assumed mean right atrial pressure in mmHg

Body Surface Area (BSA) in m²
 BSA = 0.007184 x (height in cm^{0.725} x weight in kg^{0.425})

_

viii BSA derived from height and weight reported on the site eCRF

MDT18065EVR009 Version 5.0 06-Oct-2023

Page 93 of 121

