3.0 Efficacy Event Definitions

PROSTHETIC VALVE DYSFUNCTION	
Stenosis: moderate/severe	
	Any of the following
	1) Peak aortic velocity >4 m/s OR mean aortic gradient >40 mmHg, AND EOA <0.8 cm ² .

MDT18065EVR009 Version 5.0 06-Oct-2023 Page 109 of 121

PROSTHETIC VALVE DYSFUNCTION		
	2) Peak aortic velocity >4 m/s OR mean aortic gradient >40 mmHg, AND EOA ≥0.8 cm², and DVI <0.25,	
	3) Peak aortic velocity ≤ 4 m/s and mean aortic gradient ≤ 40 mmHg, AND EOA < 0.8 cm ² , and DVI < 0.25	
Paravalvular regurgitation: moderate	Moderate paravalvular regurgitation (per echo criteria in CIP, Table 8)	
Paravalvular regurgitation: severe	Severe paravalvular regurgitation (per echo criteria in CIP, Table 8)	
Transvalvular regurgitation: moderate	Moderate transvalvular regurgitation (per echo criteria in CIP, Table 8)	
Transvalvular regurgitation: severe	Moderate or severe transvalvular regurgitation (per echo criteria in CIP, Table 8)	
Total regurgitation: moderate	Moderate total regurgitation (per echo criteria in CIP, Table 8)	
Total regurgitation: severe	Severe total regurgitation (per echo in CIP, Table 8)	

Notes:

- 1. DVI = Doppler Velocity Index (LVOT VTI/valve VTI)
- 2. For subjects with BSA <1.6 m², the EOA criteria for significant (moderate or severe) stenosis is <0.6 cm²
- 3. For subjects LVOT diameter >2.5 cm, the DVI criteria for significant (moderate or severe) stenosis is 0.2
- 4. Reporting of prosthetic valve dysfunction will be based on echo (if available).
- 5. Prosthetic valve dysfunction events are not reported as adverse events, unless the dysfunction is accompanied with clinical sequelae at the time of event detection, and the clinical sequelae are chronologically and physiologically associated with the dysfunction. However, prosthetic dysfunctions that are associated with adverse events, and that meet the definition of a serious adverse event, should be reported as such.

MDT18065EVR009 Version 5.006-Oct-2023 Page 110 of 121

Classification of Causal Relationships 4.0

The following definitions are intended as guidelines for classifying causal relationships between the event and the TAV, the delivery catheter system, and the TAVR implant procedure. Timeframe for assessing implant procedure relationships begins when the subject is being prepared for the TAVR implant (or re-implant) procedure.

Causai relationships be	tween event and the TAV	

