#### 8. Prosthetic valve thrombosis at 30 days, 6 months, one year, and annually through 5 years

Event rate estimates will be provided at 30 days, 6 months, 1 year and annually through 5 years for the attempted implant set. The outcome is descriptive including Kaplan-Meier rates and no statistical hypothesis test is specified.

9. Valve-related dysfunction, defined as moderate or severe prosthetic valve stenosis, or moderate or severe prosthetic regurgitation (per VARC II) at one year and annually through 5 years

Event rate estimates will be provided at 1 year and annually through 5 years for the implanted set. The outcome is descriptive including proportion rates and no statistical hypothesis test is specified.

10. Valve-related dysfunction requiring repeat procedure at 30 days, 6 months, one year, and annually through 5 years

Event rate estimates will be provided at 30 days, 6 months, 1 year and annually through 5 years for the attempted implant set. The outcome is descriptive including Kaplan-Meier rates and no statistical hypothesis test is specified.

- 11. Valve hemodynamic performance metrics by Doppler echocardiography at one year and annually through 5 year
  - a. Mean aortic gradient
  - b. Effective orifice area
  - c. Degree of aortic regurgitation (transvalvular, paravalvular, total)

The echocardiographic measurements will be reported at 1 year and annually through 5 years for the implanted set with site-reported echocardiographic data. No statistical hypothesis test is specified.

For mean gradient and effective orifice area, the descriptive statistics (mean, median, standard deviation, minimum, maximum and interquartile ranges) will be presented.

Degree of aortic regurgitation will be reported as proportions.

12. New York Heart Association (NYHA) functional classification at 30 day, 6 months, one year and annually through 5 years

[figure not shown]
NYHA classifications will be summarized with frequencies and percentages at 6 months, one year and annually through 5 years. All attempted implant subjects with available NYHA collections (I/II/III/IV) will be included in the analysis. No statistical hypothesis test is specified.

13. Post-operative EQ-5D quality of life at 30 days and one year

EQ-5D will be summarized with means, medians, standard deviations, minimums, maximums, and interquartile ranges, at 30 days and 1 year for the attempted implant set. No statistical hypothesis test is specified.

Revision 3.0

Page 23 of 23

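### For subjects with BSA below 1.6 m², the high-gradient stenosis criteria, read literally, leave EOA 0.6 to below 0.8 cm² unclassified, because Note 2 moves only one side of the 0.8 cm² boundary

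*Protocol*

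**What the plan says.** CIP Appendix V, section 3.0 (Efficacy Event Definitions), classes a prosthesis as moderately or severely stenosed if any of three criteria is met:

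- Criterion 1: velocity above 4 m/s or mean gradient above 40 mmHg, with EOA below 0.8 cm².
- Criterion 2: "Peak aortic velocity >4 m/s OR mean aortic gradient >40 mmHg, AND EOA ≥0.8 cm², and DVI <0.25".
- Criterion 3: velocity and mean gradient both at or below those limits, with EOA below 0.8 cm² and DVI below 0.25.

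Two notes modify the cuts. Note 2: "For subjects with BSA <1.6 m², the EOA criteria for significant (moderate or severe) stenosis is <0.6 cm²". Note 3: "For subjects LVOT diameter >2.5 cm, the DVI criteria for significant (moderate or severe) stenosis is 0.2".

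The definition feeds item 9 of the other outcome measures, valve-related dysfunction (CIP 9.1.1.4; SAP 7.10.5). The SAP plan for item 9 is: "Event rate estimates will be provided at 1 year and annually through 5 years for the implanted set". It reports proportions, refers to VARC II and gives no stenosis algorithm of its own. Under SAP 7.5.1, echo data after 30 days are site-reported. Under CIP 9.2.5, EOA, DVI and BSA are derived in the central database.

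**The concern.** Criteria 1 and 2 are built as complements. Above the gradient limits, a valve with EOA below 0.8 cm² is stenotic outright, and one with EOA of 0.8 cm² or more is stenotic if DVI is also low. Note 2 restates only the lower side for small subjects. The lower bound in criterion 2 is left at 0.8 cm², so the two criteria no longer meet. Criterion 3 cannot help, because it requires a low gradient.

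At stake is the stenosis part of item 9, which is still being collected: the last implant was in February 2023 and the outcome runs to five years. A programmer has to turn this text into a rule, and the literal text and the likely intent give different answers for the same valve. Under Note 5 of the same section, dysfunction without clinical sequelae is not reported as an adverse event, so a silent stenosis missed by the rule would have no adverse event record behind it.

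**Working it through.** The plan states no figure to reproduce; this is a check of a classification rule.

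**Inputs.** Criteria 1 to 3 with Notes 2 and 3 (CIP Appendix V, 3.0). EOA = 0.785 × LVOT² × DVI, and BSA = 0.007184 × height^0.725 × weight^0.425 (CIP Appendix II, 5.0). DVI is the ratio of LVOT VTI to valve VTI in both appendices, so for a given LVOT diameter EOA and DVI move together.

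**Step 1: the literal rule for BSA below 1.6 m².** Let H mean velocity above 4 m/s or mean gradient above 40 mmHg.

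- Criterion 1: H and EOA < 0.6
- Criterion 2: H and EOA ≥ 0.8 and DVI < 0.25
- Criterion 3: not H, EOA < 0.6 and DVI < 0.25

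If H is true, only criteria 1 and 2 can apply, and 0.6 ≤ EOA < 0.8 is covered by neither. For BSA of 1.6 m² or more, criterion 1 is H and EOA < 0.8, and there is no gap.

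**Step 2: can a valve fall in the gap?** DVI < 0.25 implies EOA < 0.785 × 0.25 × LVOT² = 0.19625 × LVOT².

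- EOA can reach 0.6 only if LVOT exceeds √(0.6/0.19625) = 1.75 cm.
- EOA can reach 0.8 only if LVOT exceeds √(0.8/0.19625) = 2.02 cm. Below that, literal criterion 2 can never be met.

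| LVOT (cm) | 0.785 × LVOT² | DVI range in the gap |
|---|---|---|
| 1.9 | 2.83 | 0.212 to <0.25 |
| 2.0 | 3.14 | 0.191 to <0.25 |
| 2.2 | 3.80 | 0.158 to 0.211 |
| 2.6 (DVI cut 0.2, Note 3) | 5.31 | 0.113 to 0.151 |

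**Step 3: behaviour within one subject.** Take BSA below 1.6 m² and a high gradient, with LVOT 2.2 cm:

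| DVI | EOA = 3.80 × DVI (cm²) | Literal class |
|---|---|---|
| 0.22 | 0.84 | stenosis (criterion 2) |
| 0.20 | 0.76 | not stenosis |
| 0.15 | 0.57 | stenosis (criterion 1) |

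The class reverses as obstruction worsens. At LVOT 2.0 cm there is no reversal: DVI 0.22 gives EOA 3.14 × 0.22 = 0.69 and meets no criterion, and the valve is classed as stenotic only once DVI falls below 0.191.

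**Step 4: direction.** Replace 0.8 by 0.6 in all three criteria. Criteria 1 and 3 are as in Step 1, and criterion 2 becomes EOA ≥ 0.6, which contains EOA ≥ 0.8. Every valve caught by the literal rule is therefore still caught, so the literal count cannot exceed the complementary one.

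**Step 5: does Note 2 apply to plausible body sizes?** The documents give no BSA distribution. For illustration only, 155 cm and 55 kg gives 1.53 m²; 160 cm and 55 kg gives 1.56 m²; 160 cm and 60 kg gives 1.62 m².

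**The case against.** The strongest reply is that Note 2 is not confined to criteria 1 and 3. It speaks of the EOA criteria in general, and the 0.8 in criterion 2 is merely the complement of the 0.8 in criterion 1, so moving one moves both and no gap exists. That is probably the intent, and it stands as a reason not to claim that subjects will be misclassified. But the note gives a direction (below 0.6 cm²), not a bare cut-off as Note 3 does. Put literally into criterion 2, it would make every high-gradient valve with EOA of 0.6 cm² or more non-stenotic. Three readings give different answers, and neither document chooses.

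Punctuation also matters. The working groups velocity or gradient together before the EOA condition, as the comma suggests. If AND is bound before OR, velocity above 4 m/s qualifies alone, and the gap remains only for a gradient above 40 mmHg with velocity at or below 4 m/s.

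Two stronger readings are tempting. First, a reader might hold DVI at 0.22 and note that EOA 0.85, 0.70 and 0.55 cm² are classed as stenosis, not stenosis and stenosis. By the CIP formula those need LVOT diameters of 2.22, 2.01 and 1.78 cm, so they are three anatomies, not one worsening valve; the reversal within a subject needs an LVOT above about 2.02 cm. Second, a reader might count all subjects with BSA below 1.6 m² as affected and conclude that the trial's durability result is biased. Note 2 governing a subject does not put that subject's valve in the gap, which also needs a high gradient, a low DVI and EOA in the band. A different class at the same EOA in a larger subject is no evidence either, since adjusting for body size is what Note 2 is for.

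The outcome's standing is limited too. Item 9 is one of 13 descriptive other measures. Item 11 still reports mean gradient and EOA, item 10 captures repeat procedures, and moderate or severe regurgitation still counts in item 9. No primary or secondary endpoint uses these criteria.

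**Conclusion.** The drafting gap is real and should be closed. On the literal text, with velocity and gradient grouped, a high-gradient valve with DVI below 0.25 and EOA from 0.6 to below 0.8 cm² in a subject with BSA below 1.6 m² meets no stenosis criterion. The gap can be reached at LVOT diameters above about 1.75 cm. Above about 2.02 cm the class can reverse within one subject.

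The documents do not show that any subject is or will be misclassified, nor that the literal rule has been programmed. If it is, the stenosis part of item 9 can only be under-counted relative to the complementary reading. How many subjects would be affected is unknown and may be zero. One such case would move the rate by 1/50 = 2 percentage points if all 50 primary subjects had an evaluable echo, and by more with fewer echoes.

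**What to change.** Reconcile Note 2 with criterion 2 in CIP Appendix V, 3.0, so that the two high-gradient criteria stay complementary for BSA below 1.6 m². The direct way, subject to the sponsor confirming that this is the intent, is to say that the Note 2 cut replaces 0.8 cm² wherever it appears in criteria 1 to 3. This introduces no new threshold; whether the cut itself is clinically right is not judged here. State the same rule in the SAP derivation for 7.10.5 item 9, with the grouping of velocity and gradient made explicit.

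The cost is one line in each document, with no new data or visits. The downside is that the reported dysfunction rate may be slightly higher.

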APPENDIX VII: SAMPLE INFORMED CONSENT FORM

Sample Informed Consent Form will be provided in a separate cover.

MDT18065EVR009 Version 5.0 06-Oct-2023

Page 115 of 121

28. Version History

Version	Summary of Changes	Author(s)/Title
1.0	Not Applicable, New Document	
2.0	 Sections 6.0 and 7.2.1: Revised to correct outer wrap description from 2.0 to 1.5 cells. Rationale: align with engineering documents and IB. Section 7.2.3 Figure 2: Corrected loading system name from Evolut PRO to EnVeo PRO Section 16.6: Removed reference to "AE code list' and added 'The AE code list will be provided under a separate cover.' Section 16.7.3, Table 5: Removed 'with SADE potential' as the Investigator should submit all AEs and DDs to Medtronic Section 21.1: Added 'The cost of the medical check-ups which are required by the study will be reimbursed as well.' for consistency with the Patient Informed Consent Form Minor formatting changes throughout 	
3.0	 Cover and Content: Updated lead site name, lead site investigator, the co-investigator Section 5.3: deleted "vendor". Section 9.1.1.4: Other Outcome Measures Added New York Heart Association (NYHA) functional classification at 30days. Section 9.2.7.5 and 9.2.7.6: Revised the paragraph for Device Malfunction or Explant. 	

	 Section 9 (including fig.4): Added the point of screening and revised the point of enrollment and the related sections. Content: Revised "AE" to "Ae", "Ec" to "EC". Fig1 and Appendix VI: STUDY CONTACTS: Delete Pathology Core Laboratory; Update Monitoring & Site Management. Appendix V: revised "Moderate paravalvular regurgitation" to "Moderate transvalvular regurgitation". 	
4.0	 Investigational Product Registration Approval Status Update Device Success Analysis Cohort Correction Supplemental Definitions for CIP Appendix V, Section 2.0- Other TAVI- related Complications Updated all relevant sections to align with requirements of new NMPA GCP for Medical Devices Fig1 and Appendix VI: STUDY CONTACTS: Delete Wuxi Clinical Development Services and replace with Medtronic Core Clinical Solutions. Miscellaneous administrative updates/corrections throughout 	
5.0	 Study design transferred from a premarket to a post-market study Deleted Echo Core lab Safety reporting update from collecting all AEs to only collect SAEs, index procedure and/or device related AEs and safety endpoint AEs (Refer to Appendix V Safety Endpoint Definitions Safety Endpoint Definitions) 	

#### **Version History** 1.

| Version | Summary of Changes   | Author(s)/Title |
|---------|--|-----------------|
| 1.0     | Initial release  |                 |
| 2.0     | 
 
Moved text from Section 7.3 to Section to Section 5 and updated Section 7.3.
 
Removal of Figure 1 Flow chart of study entry process and associated text. This flow chart is in the CIP and is not necessary to include in SAP.
 
Clarified disposition of subjects in Section 7.1.1.
 
Modified the K-M method in Section 7.2.2.
 
Added Per-Protocol set in Section 7.1.3.
 
Removed NMPA submission language.
 
Updated the analysis set for Device success.
 
Added sensitivity analysis to Sections 7.9.1 and 7.9.2.
 
 |                 |
| 3.0     | 
 
Updated wording in following sections to post-marketing and to align with CIP 5.0         
 
Section 3.
 
Section 5.
 
 
 
Updated following sections regarding the use of echocardiographic data         
 
Added section 7.5 Use of Echocardiographic Data
 
Wording in section 5.1
 
 
 
Updated for clarity in section 7.1.3, 7.2.1, 7.2.2, 7.4, 7.10, 8.
 
Replaced duplicate wording in section 7.7 and 7.8 with reference to section 7.2.1
 
Minor formatting updates throughout
 
              |                 |

#### **List of Abbreviations and Definitions of Terms** 2.

| Term/Acronym | Definition                   |  |  |  |
|--------------|------------------------------|--|--|--|
| AE           | Adverse event                |  |  |  |
| AS           | Aortic stenosis              |  |  |  |
| AVR          | Aortic valve replacement     |  |  |  |
| BAV          | Balloon aortic valvuloplasty |  |  |  |
| CEC          | EC Clinical Events Committee |  |  |  |

Revision 3.0

Page 5 of 23

| Term/Acronym                   | Definition   |  |  |  |
|--------------------------------|--|--|--|--|
| CIP                            | Clinical Investigation Plan  |  |  |  |
| CVA                            | Cerebrovascular accident   |  |  |  |
| EOA                            | Effective orifice area   |  |  |  |
| EOAI                           | Effective orifice area index   |  |  |  |
| ERC                            | Eligibility Review Committee   |  |  |  |
| ніт/ніттѕ                      | Heparin-Induced Thrombocytopenia / Heparin-Induced Thrombocytopenia and Thrombosis |  |  |  |
| ICD                            | Implantable Cardioverter Defibrillator   |  |  |  |
| LBBB                           | Left bundle branch block   |  |  |  |
| LVEF                           | Left ventricular ejection fraction   |  |  |  |
| NMPA                           | National Medical Product Administration  |  |  |  |
| NYHA                           | New York Heart Association   |  |  |  |
| PROM                           | Predicted risk of mortality  |  |  |  |
| RBBB                           | Right bundle branch block  |  |  |  |
| SAVR                           | Surgical aortic valve replacement  |  |  |  |
| STS                            | Society of Thoracic Surgeons   |  |  |  |
| TAV Transcatheter aortic valve |  |  |  |  |
| TAVI                           | Transcatheter aortic valve implantation  |  |  |  |
| TAVR                           | Transcatheter aortic valve replacement   |  |  |  |
| TEE                            | Transesophageal echocardiology   |  |  |  |
| TIA                            | Transient ischemic attack  |  |  |  |
| TTE                            | Transthoracic echocardiography /echocardiogram                                     |  |  |  |
| VARC                           | II Valve Academic Research Consortium II   |  |  |  |
| WBC                            | White blood cell   |  |  |  |

#### **Introduction** 3.

This Statistical Analysis Plan has been designed to document, before data are analyzed, the rationale for the study design, and the planned analyses that will be included in study reports. This statistical analysis plan is developed based on the Clinical Investigational Plan (CIP) Revision 5.0. As of CIP 5.0, the study transitioned to the post-market phase.

The purpose of this study is to evaluate the safety and efficacy of the Medtronic CoreValve™ Evolut™ PRO System when used by Chinese implanting centers in patients with severe symptomatic aortic stenosis (AS) who are at high risk for Surgical Aortic Valve Replacement (SAVR). The study population will include males and females with severe symptomatic aortic stenosis who are considered at high risk for SAVR. This is a prospective, observational, single arm, interventional, multi-center, post-market study.

Revision 3.0

Page 6 of 23

Data will be analyzed and Clinical Study Reports (CSRs) will be prepared for the primary endpoint (at 30 days) and annually through 5 years. The final analysis will be performed when all implanted subjects have completed their 5-year follow-up.

#### 4. **Study Objectives**

The objective of this clinical study is to evaluate the safety and efficacy of the Medtronic CoreValve™ Evolut™ PRO System when used by Chinese implanting centers in patients with severe symptomatic aortic stenosis (AS) who are at high risk for Surgical Aortic Valve Replacement (SAVR).

## 4.1 Primary Endpoints

The following primary endpoints will be used to evaluate the study objective:

All-cause mortality at 30 days

Efficacy

[figure not shown]
The percentage of evaluable echocardiograms with moderate or severe aortic regurgitation at 30 days by transthoracic echocardiography (TTE).

## **4.2 Secondary Endpoints**

The following secondary endpoints will be used to evaluate the study objective:

- Safety
  - 1) The VARC II Combined Safety Endpoint at 30 days, which includes the following components:
    - All-cause mortality
    - All stroke (disabling and non-disabling)
    - Life-threatening bleeding
    - Acute kidney injury: stage 2 or 3 (including renal replacement therapy)
    - Coronary artery obstruction requiring intervention
    - Major vascular complication
    - Valve-related dysfunction requiring repeat procedure (BAV, TAVI, or SAVR)
  - 2) Event rates of the individual components of the VARC II composite safety endpoint at 30 days
  - 3) New permanent pacemaker at 30 days
- Efficacy
  - 1) Device success at 24 hours to seven days, defined as:
    - Absence of procedural mortality, AND
    - Correct positioning of a single prosthetic heart valve into the proper anatomical location, AND

Revision 3.0 Page 7 of 23

[figure not shown]

- o Intended performance of the prosthetic heart valve, defined as the absence of patient prosthesis-mismatch and mean aortic valve gradient less than 20 mmHg (or peak velocity <3m/sec), AND
- absence of moderate or severe prosthetic valve regurgitation
- 2) Valve performance parameters at 30 days by transthoracic echocardiography (TTE):
  - Mean aortic gradient
  - Effective orifice area
  - Degree of aortic regurgitation (transvalvular, paravalvular, total)

